10.2 Serious Adverse Experiences (SAE)

An SAE is defined as any AE occurring at any dose that results in any of the following outcomes:

- death
- a life-threatening adverse experience
- inpatient hospitalization or prolongation of existing hospitalization
- a persistent or significant disability/incapacity
- a congenital anomaly/birth defect

Other important medical events may also be considered an SAE when, based on appropriate medical judgment, they jeopardize the subject or require intervention to prevent one of the outcomes listed.

10.2.1 Serious Adverse Experience Reporting

Study sites will document all SAEs that occur (whether or not related to study drug) per [UCSF HRPP Guidelines](#). The collection period for all SAEs will begin after informed consent is obtained and end after procedures for the final study visit have been completed.

In accordance with the standard operating procedures and policies of the UCSF Institutional Review Board (IRB), the site investigator will report SAEs immediately to the UCSF IRB and sponsor.

10.3 Protocol Defined Important Medical Findings Requiring Real Time Reporting

N/A

11 DISCONTINUATION AND REPLACEMENT OF PARTICIPANTS

11.1 Early Discontinuation of Study Drug

A subject may be discontinued from study treatment at any time if the subject, the investigator, or the Sponsor feels that it is not in the subject's best interest to continue. The following is a list of possible reasons for study treatment discontinuation:

- Subject withdrawal of consent
- Subject is not compliant with study procedures
- Adverse event that in the opinion of the investigator would be in the best interest of the subject to discontinue study treatment
- Protocol violation (falsifying eligibility criteria) requiring discontinuation of study treatment
- Lost to follow-up
- Positive pregnancy test (females)

If a subject is withdrawn from treatment due to an adverse event, the subject will be followed and treated by the Investigator until the abnormal parameter or symptom has resolved or stabilized.

All participants who discontinue study treatment should come in for an early discontinuation visit as soon as possible and then should be encouraged to complete all remaining scheduled visits and procedures.

All participants are free to withdraw from participation at any time, for any reason, specified or unspecified, and without prejudice.

Reasonable attempts will be made by the investigator to provide a reason for subject withdrawals. The reason for the subject's withdrawal from the study will be specified in the subject's source documents.

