EFFICACY EVALUATIONS	Validated laryngology PROMs, voice analysis via mobile app (voice recording sample), duration of effect
PRIMARY ENDPOINT	Efficacy, measured quantitatively through VHI-10 questionnaires
SECONDARY ENDPOINTS	Duration of benefit, assessed qualitatively through phone call surveys
OTHER EVALUATIONS	Participant Questionnaires CPIB-10 OMNI-VES EAT-10

	Clinician Scales Unified spasmodic dysphonia rating scale (USDRS) Phonalyze
SAFETY EVALUATIONS	Incidence of adverse events
PLANNED INTERIM ANALYSES	When approximately 50% of patients have completed the study's initial injection, an interim analysis for safety will be conducted.
STATISTICS Primary Analysis Plan	Safety profile including AE and SAEs will be reported. Simple descriptive statistics will be used to summarize toxicities in terms of type, severity and minimum or maximum values for laboratory measures, time of onset, duration, and reversibility or outcome. Tables will be created to summarize these toxicities and side effects. Safety Analyses will be performed on Safety Analysis Set.
Rationale for Number of Subjects	A sample size of 20 will provide 80% power to detect a difference of 6.6 at a significance threshold (alpha) of 0.05.

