2.1 Risk / Benefit Assessment

Risks are mitigated through the use of fellowship-trained laryngologists who are experts at this type of injection.

Possible Risks: There are risks to taking part in any research study. Some of the most likely risks of participation in this study include:

- Having no effect on voice
- Requiring multiple injections
- Injection site pain or discomfort

There are also rare but serious risks of participation, like:

- *Difficulty swallowing, possibly requiring a temporary feeding tube*
- *Difficulty breathing, possibly requiring hospitalization*

Possible Benefits:

- Participants may benefit from participating in the study, but this cannot be guaranteed. When looking at previous trials with a different indication, DAXI provided a longer-lasting effect than traditional Botox.

The potential benefits may outweigh the risks as DAXI may ultimately decrease frequency of injection, while maintaining similar risk to Botox injection.

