4 STUDY DESIGN

4.1 Study Overview

This is a single-center, open-label, dose-escalation trial. 20 subjects are planned. Each subject will be administered a single dose of DAXI. If the subject does not achieve the desired self-reported voice improvement, at 1 week post injection an additional dose of DAXI will be administered.

Screening data will be reviewed to determine subject eligibility. Subjects who meet all inclusion criteria and none of the exclusion criteria will be entered into the study.

The following treatment regimens will be used:

- Injection of DAXI at the following doses: 0.625, 1.25, 2.5 units depending on subject's current standard dose of Botox.

Total duration of subject participation will be 36 weeks. Total duration of recruitment and completion of all procedures of the study is expected to be up to 2 years.

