8.1.9 Adverse Events

Information regarding occurrence of adverse events will be captured throughout the study. Duration (start and stop dates), severity/grade, outcome, treatment and relation to study drug will be recorded on the case report form (CRF).

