9.5 Visit 4 (Phone call, Day 14*)

1. Phone call to assess clinical improvement
2. Ensure there is absence of dysphagia (using EAT-10 questionnaire), no injection site issue, or other adverse event

*Day 14 after most recent DAXI injection

9.6 Visits 5-10 (Remote Survey, every month starting 1 month after most recent injection)

1. Phone call to assess duration of benefit
2. Patient fills out PROMs electronically through Qualtrics to assess our primary (VHI-10) and secondary outcome measures

- VHI-10
 - CPIB-10
 - OMNI-VES
 - EAT-10
3. Patient records their voice in Phonalyze for CPP and CAPE-V analysis
 4. Patient will record whether DAXI still has desired effect

Data is collected monthly until loss of benefit.

For every instance when all PROMs and Phonalyze recordings are completed, patients will be paid \$10, up to \$150. After the completion of the study the number of entries will be tabulated and patient will be given a Visa gift card in the allotted amount. Patients who withdraw from the study will still be compensated for all instances when PROMs and Phonalyze recordings were completed.

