10 ADVERSE EXPERIENCE REPORTING AND DOCUMENTATION

10.1 Adverse Events

An adverse event (AE) is any untoward medical occurrence in a clinical investigation of a patient administered a pharmaceutical product and that does not necessarily have a causal relationship with the treatment. An AE is therefore any unfavorable and unintended sign (including an abnormal laboratory finding), symptom or disease temporally associated with the administration of drug product, whether or not related to that product. An unexpected AE is one of a type not identified in nature, severity, or frequency in the current Package Insert or of greater severity or frequency than expected based on the information in the Package Insert.

The Investigator will probe, via discussion with the subject, for the occurrence of AEs during each subject visit and record the information in the site's source documents. Adverse events will be recorded in the patient CRF. Adverse events

will be described by duration (start and stop dates and times), severity, outcome, treatment and relation to study drug, or if unrelated, the cause.

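### After the first month, the length of adverse-event follow-up depends on voice response, and no visible rule covers the outcome of an event still ongoing at last contact

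*Combined protocol and SAP*

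**What the plan says.** **When contacts stop.** Section 5.2 schedules calls at Day 5, at Day 14 and then monthly, ending when benefit is lost. Section 9.6 says of the monthly Visits 5-10: "Data is collected monthly until loss of benefit". The column heading for those visits in Appendix 1 says the same. No contact is scheduled after loss of benefit.

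**When safety collection stops.** Section 10.2.1 has SAE collection start at consent and "end after procedures for the final study visit have been completed". For AEs in general, section 8.1.9 says "Information regarding occurrence of adverse events will be captured throughout the study", and section 10.1 gives the method: "The Investigator will probe, via discussion with the subject, for the occurrence of AEs during each subject visit".

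**How long participation lasts.** Section 4.1: "Total duration of subject participation will be 36 weeks". The synopsis words the same 36 weeks as an upper limit.

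**What happens to ongoing events.** Section 11.1: "If a subject is withdrawn from treatment due to an adverse event, the subject will be followed and treated by the Investigator", until the problem has resolved or stabilised. Section 11.1 also asks for an early discontinuation visit, which section 9.7 marks as not applicable. Section 13 withdraws a subject at once on a further laryngeal Botox injection.

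**What will be reported.** The synopsis says toxicities will be summarised by type, severity, "time of onset, duration, and reversibility or outcome".

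**The concern.** An efficacy event decides how long a subject is observed for safety. Section 2.1 lists "Having no effect on voice" first among the most likely risks, so an early end of contact is foreseen. Section 9.4 allows a second injection when the first has insufficient effect, so a subject with more exposure can also be among those followed for the shortest time.

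Two of the promised summaries suffer. The duration and outcome of an AE still present at the last contact are unknown, and the plan does not say whether it will be counted as unresolved, as ended on that day or as censored. The incidence of later events is computed over observation times that differ between subjects and depend on response. Swallowing and breathing difficulty are the serious risks named in section 2.1, so these summaries matter.

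**Working it through.** No power or sample-size figure bears on this point. The plan's one relevant figure is the 36 weeks, so the first check is whether the visit schedule reproduces it.

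1. **Full schedule.** Visits 5-10 are six monthly contacts counted from the most recent injection. With a month taken as 28 or 30.4 days (assumption), Visit 10 falls at 6 × 28 = 168 days (24.0 weeks) or 6 × 30.44 = 182.6 days (26.1 weeks) after that injection. The latest case is a second injection on Day 14 + 2 = 16: 16 + 182.6 = 198.6 days, or 28.4 weeks from Day 0. Counting the 7 days of screening gives 205.6 days (29.4 weeks), and the ±2-day window adds at most 0.3 week. No listed visit reaches 36 weeks.

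2. **Shortest schedule.** A subject without benefit at the first monthly contact has that contact as the last: Day 28 to 30 after a single injection. After a second injection on Day 7 to 14 it is study Day 7 + 28 = 35 to 14 + 30.4 = 44.4, still about one month after the last injection.

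3. **Spread.** 168 / 28 = 6. Scheduled follow-up after the last injection can differ six-fold between subjects, according to voice response.

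4. **What is common to all.** Every subject has the Day 5 call (EAT-10 and safety survey), the Day 14 call after the most recent injection (EAT-10 and AE check) and the first monthly contact. Unequal follow-up begins after that.

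5. **What is lost.** Take an event first reported at Day 5 and still present at a last contact on Day 28 to 30. Its observed duration is 23 to 25 days, which is only a lower bound. The same event in a subject followed to Visit 10 is observed for up to about five months longer. Events that resolve before the last contact are recorded in full in both subjects.

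6. **How common unequal follow-up would be (illustration).** Assume that DAXI durations resemble the Botox figures in section 14.6. For a mean μ and SD σ, the share losing benefit before time t is Φ((t − μ)/σ) under a normal shape. The gamma version has shape (μ/σ)² and scale σ²/μ; the lognormal matches the same mean and SD. Loss before Visit 9 (t = 5 × 30.44 / 7 = 21.7 weeks) puts the last contact at Visit 9 or earlier:
   - 18.9 ± 7.2 weeks (institutional): 65% normal, 69% gamma, 71% lognormal, or 13 to 14 of 20.
   - 15.1 ± 12.3 weeks (retrospective): 71%, 77%, 81%, or 14 to 16 of 20. The normal shape fits poorly here, since it puts Φ(−15.1/12.3) = 11% of subjects below zero.

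   Loss before Month 2 (t = 8.7 weeks) gives 3% to 8% with the institutional figures and 30% to 37% with the retrospective ones. All of these are counts of subjects with shorter follow-up, not of adverse events cut off.

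7. **Ongoing events.** Treatment is one injection with an optional second at Day 7 to 14. After that no study treatment remains from which to withdraw a subject, so the condition in the section 11.1 sentence does not fit an event found at a later monthly contact. Section 11.2, on withdrawal from the study, has no AE follow-up rule.

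**The case against.** The main structured safety checks, at Day 5 and Day 14, do not depend on response, and a monthly contact follows for everyone. The trial has one arm and descriptive safety tables, so no between-arm comparison is biased. This stands, and it confines the concern to later and unresolved events. A reader might infer that poor responders have almost no safety follow-up; the schedule does not support that.

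The text also allows another reading. Section 9.6 speaks of data collection and does not define the final study visit. Loss of benefit is not a withdrawal reason in section 13. Section 4.1 would keep the subject in the study for 36 weeks, with AEs captured throughout. On that reading the difference in follow-up disappears. But no contact is scheduled that would deliver it, and the synopsis wording points the other way. What stands is that the end date is explicit for SAEs only; for other AEs it follows from asking at visits.

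Other routes may exist. Section 13 has participants' own calls to the clinic reviewed at least every two weeks, and section 10.2.1 refers to institutional guidelines. The body of section 10.4 (Medical Monitoring) was not available to this review. So the claim is that the visible text states no rule, not that no outcome would ever be recorded.

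Two stronger numerical readings also fail. Someone could turn the Month 2 shares into 1 to 7 of 20 subjects with truncated safety data. Those figures count subjects who lose benefit early, and the upper end comes from the retrospective data, which the plan's own duration calculation does not use. Nor do the documents give any figure to show that the section 11.1 sentence misses nearly every subject with an event.

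**Conclusion.** The concern holds in a limited form. After the common Day 5, Day 14 and first monthly contacts, scheduled safety follow-up depends on efficacy and runs from about 1 month to about 24 to 26 weeks after the last injection. This conflicts with the fixed 36 weeks in section 4.1, and the synopsis and section 4.1 disagree with each other. The visible text gives no rule for obtaining the outcome of an AE ongoing at last contact, except for subjects withdrawn from treatment because of it.

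The number of AEs affected cannot be estimated, because the documents give no AE rate or duration. Events that resolved before the last contact are unaffected. The direction of any effect on incidence is also unknown, since response and AE risk may be related. The visit arithmetic rests on a month of 28 to 30.4 days; the shares of subjects rest on DAXI behaving like the Botox figures in section 14.6. The change should be made, but neither the primary analysis nor the sample size depends on it.

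**What to change.** - Reconcile the synopsis and sections 4.1, 9.6, 9.7, 10.2.1, 11.1 and 13 on how long a subject is in the study, which visit is the final one, whether an early discontinuation visit exists, and what is collected after a further Botox injection.
- Define one AE/SAE data-collection period for every injected subject that does not depend on loss of benefit. The sponsor sets its length; the data can be collected by phone.
- Record the outcome of any AE ongoing at last contact. Where it cannot be obtained, report the duration as censored at that date.
- Flag events that start after later Botox, and report AE incidence over the common period.

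These are changes to data collection and reporting. A reader might want to extend the section 11.1 sentence to all ongoing events, but it also covers treatment by the investigator. That is clinical management, and no such rule is proposed here.

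The cost is protocol wording and some extra calls. With a short common period, only subjects who lose benefit early need them. With 36 weeks, essentially everyone would, because the schedule ends earlier and, on the section 14.6 figures, 93% to 99% would have lost benefit by then.

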11.2 Withdrawal of Participants from the Study

A subject may be withdrawn from the study at any time if the subject, the investigator, or the Sponsor feels that it is not in the subject's best interest to continue.

All participants are free to withdraw from participation at any time, for any reason, specified or unspecified, and without prejudice.

Reasonable attempts will be made by the investigator to provide a reason for subject withdrawals. The reason for the subject's withdrawal from the study will be specified in the subject's source documents.

11.3 Replacement of Participants

N/A

12 PROTOCOL VIOLATIONS

A protocol violation occurs when the subject or investigator fails to adhere to significant protocol requirements affecting the inclusion, exclusion, subject safety and primary endpoint criteria. Protocol violations for this study include, but are not limited to, the following:

- Failure to meet inclusion/exclusion criteria
- Failure to report an AE

Failure to comply with Good Clinical Practice (GCP) guidelines will also result in a protocol violation. The Investigator will determine if a protocol violation will result in withdrawal of a subject.

When a protocol violation occurs, it will be discussed with the investigator and a Protocol Violation Form detailing the violation will be generated. This form will be signed by a Sponsor representative and the Investigator. A copy of the form will be filed in the site's regulatory binder and in the Sponsor's files.

13 DATA SAFETY MONITORING

A Data Monitoring Committee (DMC) to review data relating to safety and efficacy, to conduct and review interim analyses, and to ensure the continued scientific validity and merit of the study, according to the UCSF IRB. The DMC will be made up of the investigator team (PI, other study clinicians, and research assistants) will be meeting at least every 2 weeks to review preliminary data. At this time, the following will be reviewed:

- Enrollment (number of participants)

- Adverse events
- Any unexpected voice/swallow/breathing problems based on the survey data collected
- Any phone calls by participants to the Voice and Swallowing Center
- Breaches of confidentiality
- Unanticipated problems

This information will be shared with the UCSF IRB every 6 weeks. If there are any adverse events or unanticipated problems, this will be communicated immediately. An interim analysis will be conducted and reported three months after the study start date, or after the 10th subject is recruited, whichever comes first. Any participants whose confidentiality has been breached will be notified as soon as possible.

A study subject's participation in the trial will be withdrawn immediately for any the following criteria:

- The patient wishes to end participation
- The patient undergoes an additional laryngeal Botox injection (at UCSF or elsewhere)
 - Unrelated medical event/condition which impacts voice/swallowing
- The trial will be halted immediately for any of the following events:
 - If a pattern of poor clinical outcomes is seen
 - For multiple adverse events
 - At UCSF IRB discretion

Based on UCSF IRB guidelines, this trial does not meet criteria for a Data Safety Monitoring Board, although one would be assembled if requested by the UCSF IRB. The study has none of the following features:

- There is a significant likelihood of a serious adverse event to participants
- The study is conducted at multiple sites and the level of risk is greater than minimal
- The study generates data that are blinded or randomized
- The study involves a large number of patients randomized to one of two or more interventions

- A study for which the performance of an interim analysis is crucial for the protection of the participants
- First use in humans
- First use in children
- The study involves gene therapy, stem cell therapy, or other novel interventions for which long-term outcome data are not known or available

14 STATISTICAL METHODS AND CONSIDERATIONS

Prior to the analysis of the final study data, a detailed Statistical Analysis Plan (SAP) will be written describing all analyses that will be performed. The SAP will contain any modifications to the analysis plan described below. Discuss with statistician

14.1 Data Sets Analyzed

All eligible patients who are in study and receive at least one dose of DAXI will be included in the safety analysis.

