5.7 Exclusion Criteria

- Age <18
- Other neurologic conditions (ALS, Parkinson's disease, essential tremor, Meige syndrome, etc.)
- Pregnant, breastfeeding, or unwilling to practice birth control during participation in the study.
- Presence of a condition or abnormality that in the opinion of the Investigator would compromise the safety of the patient or the quality of the data.
- Naive from other types of Botox for 6 months including BotoxA

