9 EVALUATIONS BY VISIT

9.1 Phone Screening (7 Days prior to injection)

1. Confirmation participants meet all inclusion criteria and no exclusion criteria review
2. If they have provided consent to contact, reach out and explain the study to them.
3. Review the study with the subject (subject's legal representative) and obtain written informed consent and HIPAA authorization via DocuSign.
4. Assign the subject a unique screening number.
5. Record demographics data.
6. Record medical history, including history of ADLD, diagnosis date, and prior Botox treatments.
7. Patient fills out baseline PROMs electronically through Qualtrics (VHI-10, CPIB-10, OMNI-VES, EAT-10)
8. Patient records their voice in Phonalyze for CPP and CAPE-V analysis

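### Section 14.1 makes eligibility a condition of the safety set, so on its plain reading a DAXI-treated subject later found ineligible drops out of the adverse event tables

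*Combined protocol and SAP*

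**What the plan says.** Section 14.1 of the combined protocol and SAP states: "All eligible patients who are in study and receive at least one dose of DAXI will be included in the safety analysis". This is the only place where the set is defined. The synopsis, under its primary analysis plan, says "Safety Analyses will be performed on Safety Analysis Set" without saying who belongs to it. The synopsis also plans that, once about half the patients have had their initial injection, "an interim analysis for safety will be conducted".

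Section 5.5 gives *eligible* a meaning: having the diagnosis and meeting the inclusion criteria and none of the exclusion criteria. Section 4.1 describes entry: "Subjects who meet all inclusion criteria and none of the exclusion criteria will be entered into the study".

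Two sections allow for that process to fail. Section 12 lists "Failure to meet inclusion/exclusion criteria" among the protocol violations. Section 11.1 lists, among the reasons to stop treatment, "Protocol violation (falsifying eligibility criteria) requiring discontinuation of study treatment". Neither says whether the subject stays in the safety set.

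**The concern.** A safety set normally depends on exposure alone, because the question is what happened to the people who were given the drug. Here a stated rule adds two further conditions. If a subject is injected and a breach of the criteria then comes to light, someone following section 14.1 literally would leave that subject out of the AE tables.

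Two features make this more than a matter of tidiness. First, the trial is open-label, and section 12 leaves it to the investigator whether a violation leads to withdrawal. If eligibility also governs membership of the safety set, the wording leaves room for that judgement to be made after an AE is known. Second, one exclusion criterion in section 5.7 covers conditions that in the investigator's opinion "would compromise the safety of the patient or the quality of the data". At least some breaches could therefore involve subjects whom the protocol itself would have kept away from the drug on safety grounds.

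The phrase about being in the study is a lesser ambiguity. It most likely means entered, but it could be taken to remove subjects who have withdrawn.

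**Working it through.** The plan attaches no figure to this point. The check is first a comparison of texts, then a bound on the effect.

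**1. Does the definition depend on more than dosing?** Yes. Section 14.1 joins three conditions: eligible, in the study, at least one dose. Section 5.5 equates eligible with meeting the criteria.

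**2. Can a subject be dosed and not eligible?** Yes. Section 9.1 places the main check at a phone contact 7 days before injection: "Confirmation participants meet all inclusion criteria and no exclusion criteria review". Visit 1 (section 9.2) then lists a contraception review, a pregnancy test and a physical examination ahead of the injection. These will catch some failures, but not, for instance, a concealed history. Sections 11.1 and 12 make provision for failures that get through.

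**3. Does any other section put such a subject back into the set?** No. Sections 8.1.9 and 10.2.1 record AEs and serious AEs without regard to eligibility, and section 13 reviews AEs at least every two weeks. Those sections govern capture and reporting, not the analysis set.

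**4. Can the SAP correct it in time?** Section 14 promises a SAP before the final data are analysed. The interim safety analysis may come first, and section 14.1 would then apply as it stands.

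**5. How far can one exclusion move a rate?** Inputs: n = 20 planned subjects (synopsis, section 4.1), all assumed dosed; n = 10 for an interim at half of them; one subject excluded (assumption). Let x be the number of subjects with the AE.

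- The excluded subject had the AE: the rate falls by x/n − (x−1)/(n−1) = (n−x)/(n(n−1)). This is largest at x = 1, where it equals 1/n.
  - n = 20: 1/20 = 5.0% becomes 0/19 = 0%, a fall of 5.0 points.
  - n = 10: 1/10 = 10.0% becomes 0/9 = 0%, a fall of 10.0 points.
- The excluded subject did not have the AE: the rate rises by x/(n−1) − x/n = x/(n(n−1)).
  - n = 20, x = 1: 1/20 = 5.0% becomes 1/19 = 5.3%.
  - n = 10, x = 1: 1/10 = 10.0% becomes 1/9 = 11.1%.

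For scale, the exact (Clopper-Pearson) 95% intervals are 0.1 to 24.9% for 1/20 and 0 to 17.6% for 0/19; 0.3 to 44.5% for 1/10 and 0 to 33.6% for 0/9. The plan itself calls only for descriptive statistics, so these intervals are an addition here.

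**The case against.** The strongest reply is that the sentence includes people and does not expressly exclude anyone. It says that eligible dosed patients will be in the analysis; it does not say *only* those. Section 4.1 describes screening data being reviewed to decide eligibility, with those who pass being entered, so section 14.1 can be read as covering everyone judged eligible and entered, whatever is found later. That reading is available and lowers the certainty of the point. It does not remove it: section 5.5 defines eligibility by the criteria themselves, no section fixes it at the screening decision, and subjects outside the sole definition have no stated place in the tables.

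The sections on violations and discontinuation also do not say that data are dropped. Section 11.1 even asks that subjects who stop treatment be encouraged to complete their remaining visits. That is correct, and it means the data would exist. What is unresolved is whether they would be tabulated.

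A reader might infer that AE rates will be understated by a predictable amount. The documents do not support that. They give no number of ineligible treated subjects and no excess risk for them. The criterion on safety also covers data quality alone and rests on the investigator's opinion, and other breaches, such as an unstable BotoxA dose, are not described as safety risks. As the working shows, removing a subject without the AE raises the rate.

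Nor is an interim at 10 subjects certain. The synopsis sets it at about half the patients injected; section 13 sets it at three months or the 10th recruit, whichever comes first; section 14.5 refers to every three months. The 10 is one possibility, and the number could be smaller.

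**Conclusion.** The point holds as a minor defect in a stated rule. On its plain reading, section 14.1 puts a DAXI-treated subject later found ineligible outside the safety tables; the reading as judged eligible and entered is possible but not secured by the text.

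The consequence is limited to the descriptive AE summaries. The worst case for one excluded subject is 5.0 points at n = 20 and 10.0 points at an interim of 10. This assumes that all planned subjects are dosed and that the excluded subject is the only one with the event. No expected bias should be quoted, because neither the count of such subjects nor the average direction of the effect can be obtained from the documents.

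A reader might also infer that harms would go unreported or that the halting rules would be weakened. They would not: AE capture, serious AE reporting to the IRB and the two-weekly review on which halting rests do not use this set. The efficacy test and the sample size are likewise unaffected.

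**What to change.** Reword section 14.1 to: *The safety set is all subjects who receive any DAXI, regardless of eligibility or later withdrawal.* State that the same set serves the interim and the final safety analyses, and identify subjects with eligibility violations in a footnote to the AE table. This settles both the eligibility condition and the doubt about withdrawn subjects.

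The cost is one sentence, made by protocol amendment under section 16.1, or in the SAP provided the SAP is written before the interim safety analysis. No new data, visits or subjects are needed.
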